11.2.3 Disease History and Characteristics

Time since UC diagnosis (years) will be summarised for the FAS (*Table 14.1.6*) and is derived as (date of informed consent - date of UC diagnosis) / 365.25. The stratification factors, concomitant treatment with corticosteroids (yes, no) and previous biologics exposure (yes, no), will be summarised within the same table.

The faecal calprotectin levels recorded at baseline will be summarised descriptively (*Table 14.1.7*). TMS, PMS and MH and PH component summary measures from the SF-36 questionnaire collected at baseline will be also be summarised descriptively within the same table. Note that the TMS encompasses the PMS (number of stools, blood in stools and severity assessment) and the endoscopy sub-score. The baseline endoscopy is performed at screening while the PMS is assessed both during the screening and the Day

0 visits. Therefore the baseline TMS value will be derived by adding the endoscopy sub-score performed at screening with the PMS done at Day 0.

The number and proportion of patients with concomitant use of medications for UC will be summarised by all categories, some of which are corticosteroid only, immunosuppressants only, combination treatment or no treatment (*Table 14.1.8*). The number and proportion of patients with prior biological failure (categorised as TNF or others / vedolizumab) will also be presented within the same table.

11.2.4 Procedures Non-Drug Therapies

All procedures/non-drug therapies recorded on the eCRF will be listed only.

11.3 EFFICACY ANALYSES

Treatment comparisons will be ABX464 vs placebo. The main analysis set for the efficacy analyses will be the PP, and the primary analysis will be repeated for the FAS Set.

Subjects who prematurely terminate the study will be considered failures.

11.3.1 Primary Efficacy Variable

The primary efficacy endpoint, defined as the proportion of subjects receiving ABX464 with clinical remission according to the TMS at Week 8 compared to placebo, will be descriptively summarised on the PP (*Table 14.2.1.1*). Remission excludes friability and is based on the TMS being less than or equal to two, with no individual sub-score greater than one.

This response rate will be compared in subjects who received ABX464 or placebo by stratified likelihood ratio chi-square test at a one-sided 10% significance level on the PP and displayed within the same table. This table will be repeated for the FAS set (*Table 14.2.1.2*).

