9.2. Efficacy Analysis

Analysis of efficacy data will be carried out in the Full Analysis Set in which subjects who prematurely terminate the study will be considered failures.

The primary efficacy endpoint of the study, the rate of subjects responding to treatment. This response rate will be compared in subjects who received ABX464 or placebo by stratified likelihood ratio chi-square test on a 10% one-sided level.

In addition, descriptive statistics will be presented by treatment arm for all secondary efficacy variables for each measurement timepoints separately for the two study groups.

These statistics include:

- Continuous variables: mean, standard deviation, minimum and maximum, stratified 95% confidence intervals, median and quartiles will be presented.
- Categorical variables: counts, rates and stratified 95% confidence intervals for the rates will be calculated.

In addition to descriptive statistics, the following analyses will also be carried out for the variables indicated below:

- Kaplan-Meier estimates and plots will be presented for time to UC worsening after week 8.
- Mixed model analysis of covariance will be conducted for the following measurements:
 - O The change from screening in IL-22 expression levels in serum and rectal/sigmoidal tissue at week 8,
 - O The change from baseline in microRNA-124 levels in whole blood (PAXgene®) and in tissue (RNA later) at week 4 and week 8,
 - O The change from baseline in fecal calprotectin levels at week 4 and week 8,
 - O The change from screening in the histopathology/infiltrate (rectal/sigmoidal biopsies) assessed by the Geboes score at week 8,

In this model, treatments and stratum will be fixed effects, subjects will be random effect and baseline values of the respective measurements will be covariates. Other explanatory variables will also be allowed to be included in the model. In order to normalize eventual skewed distributions transformation of the data will also be considered. Study groups will be compared within this model framework. All p-values will be interpreted in a descriptive manner.

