9.3. Safety Analyses

Adverse events will be coded using the standard dictionary (MedDRA) down to the lower level term (LLT).

An overall summary table will be presented (Any adverse event, any treatment emergent adverse event (TEAE), any serious adverse event (SAE), death, any grade 3 or higher adverse events from baseline to the end of Study. This analysis will be conducted on SAF population.

Two periods will be defined for TEAE:

- Any adverse event which occurs or worsens from first dosing to Day 56;
- Any adverse event which occurs after Day 56.

Adverse events will be described by primary system organ class and preferred term. Numbers and percentage of subjects, and number of occurrence of adverse event will be presented for:

- TEAE:
- Serious TEAE;
- TEAE leading to drug discontinuation;
- TEAE of grade 3 or 4;
- TEAE for which relationship with the study drug is recorded as possible or probable.

Analysis of safety will be performed on the safety data set consisting all subjects who received at least one dose of ABX464 in the study.

Primary safety endpoint, the rate of all treatment emergent adverse experiences will be compared between the study groups by stratified likelihood ratio chi-square test on a 10% one-sided significance level.

Further assessment of safety will be based on the frequency of adverse events (with and without regard to causality) graded according to the CTC-AE Classification and also, the review of individual values for clinical laboratory data, vital signs and ECG focusing on the detection of abnormal values and PCSAs [potentially clinically significant abnormalities (PCSAs) determined upon investigator considerations].

Adverse events will be tabulated (counts and percents) by group. All adverse events will be listed and the data will be tabulated by body system/organ class. Adverse event tabulations will include all treatment emergent adverse events, which will be further classified by severity, and relationship to treatment and dose level.

Clinical laboratory parameters, vital signs, ECG will be summarized by using descriptive statistics (n, mean, SD, SEM, median, minimum and maximum). Number of subjects with at least one abnormal values will be tabulated (counts and percents) for each parameter in summary shift tables, by group and dose.

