9.4. Determination of Sample Size

The primary efficacy endpoint is the rate of subjects responding to treatment. This response rate will be compared in subjects who received ABX464 or placebo by likelihood ratio chi-square test. For the sample size assessment, the following assumptions will be made:

- Response rate (ABX464): 0.6
- Response rate (placebo): 0.2

According to literature the response rate for ABX464 treated subjects is expected to be between 50% and 75% while that in the placebo group is assumed to be approximately 10% to 20% (Gemini 1 study - N Engl J Med 2013; 369:699-710 August 22, 2013).

- Type 1 error: 10% one-sided
- Group allocation rate (ABX464 / placebo): 2:1

If the above assumptions and definitions hold true with a sample size of 30 subjects receiving ABX 464 or placebo in a ratio of 2:1 the study has 81% power to show a difference in response rate between the study groups. To gain more clinical experience with ABX464 in this indication a 2:1 randomization ratio was chosen despite the inevitable loss of power. The actual loss of power with the above assumptions is 4%. Power was computed using the normal approximation method.

Subjects who terminates the study prematurely will be considered failures therefore no adjustment for dropouts is needed.

Primary safety endpoint is the rate of all treatment emergent adverse experiences. The above sample size is sufficient to detect an increase in general treatment emergent adverse experience rate from 10% to 50% with 86% power by likelihood ratio chi-square test on a 10%, one-sided significance level.

If approximately 20 subjects receive ABX464 the study has 88% chance to detect at least 1 specific treatment emergent AE if the underlying rate of occurrence is 1:10.

When the underlying rate of occurrence is around 1:20 the sample size of 20 subjects is sufficient to observe at least 1 such an event with a probability of 64% in the active treatment group.

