3.5 SAMPLE SIZE CONSIDERATIONS

The primary efficacy endpoint is the rate of subjects responding to treatment. This response rate will be compared in subjects who received ABX464 or placebo by likelihood ratio chi-squared test. For the sample size assessment, the following assumptions will be made:

Response rate for ABX464: 0.6

• Response rate for placebo: 0.2

According to literature, the response rate for ABX464 treated subjects is expected to be between 50% and 75% while that in the placebo group is assumed to be approximately 10% to 20%.

The Type I error is defined to be one-sided 10% significance level, and the group allocation rate is 2:1 (ABX464/ placebo). If the above assumptions and these definitions hold true with a sample size of 30 subjects receiving ABX464 or placebo in a ratio of 2:1, then the study has 81% power to show a difference in response rate between the treatment groups. Power was computed using the normal approximation method. A 2:1 randomisation ratio was chosen to gain more clinical experience with ABX464 in this indication, despite the inevitable loss of power. The actual loss of power with the above assumptions is 4%.

Subjects who terminate the study prematurely will be considered failures, therefore no adjustment for dropouts is needed.

The primary safety endpoint is the rate of all treatment emergent adverse events. The above sample size is sufficient to detect an increase in general treatment emergent adverse event rate from 10% to 50% with 86% power by likelihood ratio chi-squared test at a one-sided 10% significance level.

If approximately 20 subjects receive ABX464, the study has 88% chance to detect at least I specific treatment emergent adverse event if the underlying rate of occurrence is 1:10. When the underlying rate of occurrence is around 1:20 the sample size of 20 subjects is sufficient to observe at least I such an event with a probability of 64% in the active treatment group.

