3.6 RANDOMISATION

The Investigator will need to confirm subject eligibility based on procedures performed at the Day -14 visit. If a subject is eligible, they will be randomised using the eCRF and treatment numbers will be allocated immediately. The randomisation procedure does not require a site visit by the subject.

A pre-defined randomisation list will be created by SODIA, and will be centrally managed by a block of three using a 2:1 ratio, where for every two subjects randomised to receive ABX464, one subject will be randomised to receive placebo. Randomisation will be stratified according to concomitant treatment with corticosteroids (yes, no) and previous biologics exposure (yes, no).

A total of 30 patients will be randomised. A subject who prematurely exits the study for a non-drug related reason, will be replaced. In this event, an additional subject will be randomised and will receive the next treatment allocation. This may or may not be the same treatment as that of the withdrawn subject.

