If changes in severity for the same TEAE have been reported separately but with the same adverse event (AE) number, they will be collapsed to a single AE with maximum severity for the summary tables, but listed as reported.

Classifications of medical history, concomitant medication and adverse events will be sorted alphabetically within the summary tables.

If any laboratory assessments are repeated at the same visit, the result from the repeat assessment will be used in summaries. Both values will be listed.

Data collected on the eCRF will be presented within data listings. The data listings will be sorted by treatment group, country, centre number, patient number and visit/week/day. Treatment group will be as allocated (randomised). If any patients receive the wrong treatment this will be flagged in all listings. Visits outside the visit windows will be identified within the listings.

The date format for all output presentations will be 'ddMMMyyyy'.

All statistical analysis will be performed using SAS 9.3 or higher.

P-values will be rounded to four decimal places. P-values less than 0.0001 will be reported as <0.0001 in tables.

If any of the assumptions underlying the formal statistical methods proposed are violated during the analysis of the final data, alternative statistical methods will be used and any changes documented in the statistical methods section of the CSR, including the rationale for use.

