11.4 SAFETY ANALYSES

11.4.1 Adverse Events

All AEs will be classified using the version of the MedDRA coding dictionary specified in the DMP.

Events will be classified as treatment-emergent if they started or increased in severity on or after the first date and time of medication dosing at Day 0 and up to study closure or withdrawal date. If an event start date is partial, then the start day, month, year or stop date will be used to determine if the event is treatment-emergent. If the classification of the AE cannot be determined from the data available, then the event will be considered treatment-emergent.

An overall summary table will be presented for AEs occurring from baseline to the end of the study in the following categories (*Table 14.3.1.1*):

- Any adverse event;
- Any TEAE;
- Any serious adverse event (SAE);
- Any severe adverse event (Common Toxicity Criteria [CTC] grade 3 or 4);
- Death

The primary safety endpoint, the rate of all TEAEs will be compared between the treatments by stratified likelihood ratio chi-square test on a 10% one-sided significance level and presented in the same table.

TEAEs will be further classified as follows:

Severe TEAEs: Severity classified as 'severe' (Common Toxicity Criteria [CTC] grade 3 or 4) or missing.

Serious TEAEs: Serious classified as 'yes' or missing.

Drug-related TEAEs: Relationship to study drug classified as 'yes' or missing.

Serious drug-related TEAEs: Both serious and drug-related, as specified above.

TEAEs leading to study drug discontinuation: Action taken classified as 'permanent discontinuation'.

TEAEs overall and in each of the above classifications will be summarised separately for the following periods (Tables 14.3.1.2.1 and 14.3.1.2.2):

- Period 1: Adverse event occurs or worsens from first dosing to Day 56
- Period 2: Adverse event occurs after Day 56

Summaries by SOC and PT will also be presented for TEAEs in the two periods (*Tables 14.3.1.3.1.1* and 14.3.1.3.1.2). Similar tables will be presented for each of the classifications of treatment-emergent events above (*Tables 14.3.1.3.2.1* and 14.3.1.3.6.2).

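### The stratified likelihood ratio chi-square test does not hold its one-sided 10% level at this sample size: at the plan's own 10-20% control rates the true level is about 13-20%

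*SAP*

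**What the plan says.** The same test is named for both lead endpoints in both documents.

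- **Efficacy.** SAP 11.3.1: "This response rate will be compared in subjects who received ABX464 or placebo by stratified likelihood ratio chi-square test at a one-sided 10% significance level". Protocol 9.2 specifies comparison "by stratified likelihood ratio chi-square test on a 10% one-sided level".
- **Safety.** SAP 11.4.1 has the TEAE rate "compared between the treatments by stratified likelihood ratio chi-square test on a 10% one-sided significance level", and protocol 9.3 has it "compared between the study groups by stratified likelihood ratio chi-square test on a 10% one-sided significance level".
- **Shells.** The footnotes of SAP Tables 14.2.1.1 (layout shared with 14.2.1.2) and 14.3.1.1 repeat the test and level.
- **Design.** 30 subjects, 2:1, blocks of three. SAP 3.6 gives two binary stratification factors, hence four strata.
- **Planning.** Protocol 9.4 and SAP 3.5 assume 60% v 20% response (81% power) and TEAE rates of 50% v 10% (86% power). Protocol 9.4 adds: "Power was computed using the normal approximation method". SAP 3.5 gives the expected ABX464 response, "while that in the placebo group is assumed to be approximately 10% to 20" per cent.
- **Fallback.** If assumptions fail on the final data, SAP 10.1 says "alternative statistical methods will be used and any changes documented in the statistical methods section of the CSR".

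Neither document defines the stratified LR statistic, says how a one-sided p-value is taken from it, or provides a small-sample version. SAP 10.4 records no statistical issues.

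**The concern.** The LR chi-square relies on a large-sample approximation that is poor when expected counts are small. Here one arm has 10 subjects, the plan expects 1 or 2 placebo events, and the data are split over four strata. In such tables LR tends to reject too often.

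If so, a result reported as significant at one-sided 10% would carry a larger false-positive risk than the reader is told. Remission is the efficacy endpoint on which the sample size is built, so it is the result a proof-of-concept decision would lean on. SAP 10.1 does not protect against this. It names no replacement test and applies only once the final data are analysed. By then the randomisation list has been loaded (SAP 9.3), so a switch would be a post hoc choice between tests that disagree on borderline tables.

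**Working it through.** **1. Which reading fits the plan's own power.** Pooled-variance normal approximation:

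power = Φ{[(p1 − p0) − z·√(p̄(1−p̄)(1/20 + 1/10))] / √(p1(1−p1)/20 + p0(1−p0)/10)}, with p̄ = (2p1 + p0)/3.

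- Efficacy, 0.6 v 0.2, z = 1.2816: (0.4 − 1.2816 × 0.1932)/0.1673 = 0.911, power 81.9% (stated 81%).
- Safety, 0.5 v 0.1: (0.4 − 1.2816 × 0.1866)/0.1466 = 1.097, power 86.4% (stated 86%).
- At one-sided 5% the same formula gives 68.8% and 73.7%.

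The plan therefore intends a directional 10% test: reject when the ABX464 rate is higher and the LR statistic is at least 1.2816² = 1.642.

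**2. Where the excess comes from (unstratified, 20 v 10).** Take 2/20 v 0/10, with expected counts 1.333, 18.667, 0.667 and 9.333:

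- LR = 2[2 ln(2/1.333) + 18 ln(18/18.667) + 10 ln(10/9.333)] = 1.692; p = 1 − Φ(√1.692) = 0.097, significant.
- CMH: z = (2 − 1.333)/√(20·10·2·28/(30²·29)) = 0.667/0.655 = 1.018; p = 0.154.
- Fisher one-sided: C(20,2)/C(30,2) = 190/435 = 0.44.

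For 3/20 v 0/10 the p-values are 0.054, 0.102 and 0.28.

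At a common rate of 10%, the probability of 0/10 with at least 2/20 is 0.9¹⁰ × (1 − 0.9²⁰ − 20·0.1·0.9¹⁹) = 0.3487 × 0.6083 = 0.2121. The region 1/10 with at least 6/20 adds 0.0044, giving 0.2165.

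**3. Exact unstratified level, 20 v 10.**

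| Common rate | LR | CMH |
|---|---|---|
| 10% | 21.6% | 4.7% |
| 15% | 18.6% | 7.7% |
| 20% | 15.6% | 9.0% |
| 30% | 13.0% | 10.1% |
| 50% | 12.4% | 9.0% |
| 70% | 11.3% | 10.6% |
| 80% | 11.2% | 11.1% |

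Over 20 splits (17-21 v 8-11) at rates of 10, 15 and 20%, LR exceeds 10% in 60 of 60 settings (10.3-21.6%, median 15.1%). CMH exceeds 10% in 23 of 60 (3.6-12.5%, median 9.5%). LR is above CMH in all 60.

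**4. Stratified, as planned.** Simulation with four strata, blocks of three, 2:1, and 40,000 trials per cell (Monte Carlo SE about 0.2 points). Assumed stratum sizes: A 8/8/7/7, B 13/8/6/3, C 16/9/4/1. Two forms of the stratified LR were run, because the documents define neither: unconditional (stratum-adjusted logistic model) and conditional (stratum totals fixed). Levels with all 30 subjects, at common rates of 10/15/20%:

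| Layout | Unconditional LR | Conditional LR | CMH |
|---|---|---|---|
| A | 19.6 / 17.4 / 14.8 | 15.6 / 15.2 / 13.3 | 7.7 / 10.2 / 10.6 |
| B | 19.2 / 17.6 / 14.4 | 16.2 / 15.5 / 12.6 | 7.3 / 9.9 / 9.9 |
| C | 18.2 / 17.0 / 14.2 | 14.7 / 15.2 / 13.2 | 6.4 / 9.4 / 9.9 |

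The Per Protocol (PP) set is the main efficacy set (SAP 11.3), so losses of 10% and 20% were added. Over 3 layouts × 3 losses × 3 rates × 2 forms = 54 combinations, LR runs from 12.6 to 19.6%; CMH runs from 5.5 to 10.6%. At rates of 30-80%, unconditional LR is 11.7-14.2%, conditional LR 10.1-12.2% and CMH 9.9-11.3%. A separate run with other stratum shares gave 14.2-18.9% (unconditional) and 12.7-16.5% (conditional) at 10-20%.

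**5. Power with all 30 subjects (layouts A, B, C).**

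| Test | 0.6 v 0.2 | 0.5 v 0.1 |
|---|---|---|
| Unconditional LR | 84.6, 84.9, 82.8 | 89.0, 89.8, 88.0 |
| Conditional LR | 82.1, 82.4, 80.9 | 87.1, 87.8, 87.2 |
| CMH | 81.5, 81.6, 80.4 | 86.0, 86.6, 85.8 |
| Exact stratified | 69.0, 69.2, 66.4 | 73.5, 74.0, 73.3 |

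**6. If the software's upper-tail p ≤ 0.10 were used unhalved.** The test is then nominally one-sided 5%. Its level in the ABX464 direction is 6.0-10.1% at rates of 10-20%, and power falls to 68.2-75.0% (efficacy) and 76.3-81.4% (safety).

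**The case against.** - **The test form is undefined.** The figures assume a one-degree-of-freedom, common-odds-ratio, directional LR test. Summing LR over four strata on 4 df gave about 2-12%, and step 6 shows no material excess in the ABX464 direction. This stands as a second defect, but it does not rescue the plan. A 4-df sum has no direction, so it cannot deliver a one-sided level, and the unhalved reading loses the stated power.
- **The p-values may be descriptive.** Protocol 9.2 says p-values will be interpreted descriptively. That sentence closes the mixed-model paragraph, whereas both lead endpoints are given an explicit one-sided 10% level.
- **The worked table is knife-edge.** True in part: at a 10% rate the unstratified level falls to 12.6% at 20 v 9 and 11.5% at 19 v 9. It stays above 10% at every split examined, and the stratified result does not depend on that one table.
- **CMH is not exact either.** This stands. It reaches 12.5% unstratified at 17 v 9, and at rates of 30-80% it gains little over conditional LR.
- **For safety, the error is toward flagging harm.** This stands as mitigation. CMH gives up some sensitivity (88.0-89.8% for unconditional LR against 85.8-86.6%) but still delivers roughly the planned 86%.
- **It is a 30-subject Phase IIa trial with remission among the secondary endpoints.** Also true. It limits the consequence, not the error in the stated level.

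**Conclusion.** The concern holds. Read directionally, the specified test has a true level of about 13-20% at common rates of 10-20%, against a stated 10%. The planning arithmetic is not at fault; the choice of test is.

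The range rests on assumed stratum sizes, on PP loss independent of arm and outcome, and on two plausible forms of the stratified LR. Varying the layouts, the loss and the form did not bring the level below 12.6%. For safety, the excess matters if TEAEs are as rare as the 10% planning rate; it is small if the true rate is 30-80%, which is an assumption. This should be fixed before lock. It does not invalidate the design.

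**What to change.** Before database lock, amend SAP 11.3.1 and 11.4.1 to read, for example:

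> One-sided Cochran-Mantel-Haenszel test at 10%, without continuity correction, stratified by the factors used in the randomisation; alternative: ABX464 rate higher than placebo. The reported p-value is one-sided: half the 1-df CMH p-value if the stratified difference is toward a higher ABX464 rate, otherwise one minus half.

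Name the factors explicitly once confirmed: protocol 3.1.1 says previous TNF antagonist exposure, while SAP 3.6 says previous biologics exposure. Keep the exact stratified test as a sensitivity analysis only; its level is 0.6-5.1% and its efficacy power 66-69%. Change the test name in SAP 3.5 and in the footnotes of Tables 14.2.1.1/14.2.1.2 and 14.3.1.1. Say in the SAP that CMH is only approximately level: about 6-11% stratified, up to about 12.5% unstratified at some splits.

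**Cost.** One signed SAP amendment, with no added subjects or visits. Protocol 9.2, 9.3 and 9.4 also name the LR test. Either amend them, an administrative step with eight countries listed in protocol 4.1, or record the departure and its justification in the SAP amendment as protocol 9 requires. The second route is cheaper but leaves the two documents naming different tests.

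With all 30 subjects, CMH gives up 0.5-3.3 points of power against LR as it would actually run, and essentially none against the stated 81% and 86%. With 10% lost from the PP set, CMH efficacy power is 77-78%, and with 20% lost 72-73%. That fall comes from the analysis set; LR also drops, to 77-82% at 10% loss.
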